Expected Result: An FES paradigm involving ergometry of the upper extremities will enhance subjects' functional recovery, as measured in the clinic by neurological and anatomical indices.

VIII. INCLUSION / EXCLUSION CRITERIA

a. Inclusion criteria:

- a. Male, Female, age 18-55, all ethnic groups.
- b. Spinal Cord Injury, traumatic and non-traumatic.
- c. C1-C6 neurological level.
- d. ASIA class A or B.
- e. Chronic injury,>12 months and < 20 years from the injury.
- f. No upper-extremity electrical stimulation in the previous 4 weeks.
- g. Subjects are medically stable, with no recent (1 month or less) inpatient admission for acute medical or surgical issues.
- h. Baseline physical activity will be kept stable during the study.
- i. Pain and antispasticity medications dose will be kept stable during the study.
- j. Subjects are legally able to make their own health care decisions.

b. Exclusion criteria:

- a. Associated lower motor neuron/peripheral nerve injury in the C1-C6 levels.
- b. Presence of pacemaker.
- c. Presence of cancer.
- d. History of seizures.
- e. Women who are pregnant.

IX. SUBJECT RECRUITMENT & SCREENING**a. Subject recruitment & screening:**Recruitment scenario 1:

Patients of the ICSCI, and prior study participants will be identified as meeting the inclusion criteria by reviewing the medical records held by the ICSCI and filling out a Medical Chart Review Form. A waiver of privacy authorization will be obtained from the local IRB of Record [HIPAA Form4] prior to chart review. Patients will be told about the study during a clinical visit; they will be given a Subject Recruitment Flyer with contact information; a note of this communication will be made in the patient's medical record. Those who are interested can meet privately with, or contact later the principal investigator or study coordinator who will explain in simple terms: 1) the purpose of the research and the procedures involved, 2) potential benefits, 3) potential risks, 4) the subject's right to withdraw at any time without penalty of any sort, and 5) assurance of anonymity. If a patient indicates that he/she is no longer interested or is not eligible, the Medical Chart Review Form will be shredded.

Recruitment scenario 2:

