make a decision to participate in the study. In addition, the candidate will be allowed to discuss the study's appointment logistics with their own care providers. Any questions the potential subject has about the study will be answered. Once the potential subject agrees to participate, the subject will be enrolled and an initial visit will be set up. The subject consent will be obtained during this initial visit before the post-consent screening is performed.

In the 3 years since opening the International Center for Spinal Cord Injury (ICSCI) in 2005 (05'-08'), we have evaluated and treated over 600 new patients with longstanding SCI (White 63.57%, Black 31.69%, American Indian 0.91%, Hispanic 0.36%, Asian 0.18%, Other 3.28%). Currently we evaluate and treat over 250 new patients annually. Of the new patients with long-standing SCI, 50% are ASIA A and B and of this subgroup, over 10% have a neurological level between C1 and C6. Using projections through 08' and bases of 850 system clients, approximately 85 patients will meet the entry criteria of ASIA A-B, neurological level C1-6 proposed in our study. Furthermore, study entry does not have to be limited to clients already within our ICSCI system. Therefore, based on this availability, we do not anticipate the recruitment of patients to be a substantive barrier to recruitment for this study.

b. Target Population:

We plan to enroll up to 30 subjects with an expected accrued number of subjects of 24 (screening failure of 6). The 24 accrued subjects will be randomized in 2 groups of 12. We are anticipating an attrition rate of 4 subjects maximum.

We plan to enroll both male and female subjects, all ethnic groups.

No specific racial or ethnic groups will be targeted by our recruitment process.

Non-English speaking subjects will not be targeted by our recruitment process.

No vulnerable population is specifically targeted by our recruitment process.

Pregnant women will be excluded from this study.

c. Recruitment Material:

Subject Recruitment Flyer: form given to ICSCI patients that fit the study criteria during a clinic visit, and posted on the ICSCI website (www.spinalcordrecovery.org).

Inclusion/Exclusion Index Card: Laminated index cards with inclusion/exclusion criteria that physician can carry.

Inclusion/Exclusion Wall Listing: Laminated listing with inclusion/exclusion criteria posted in ICSCI clinic rooms that physician can refer to.

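### Does the recruitment pool of about 85 patients need correcting, given that the protocol's own percentages yield a floor of about 43?

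*Combined protocol and SAP*

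**What the plan says.** Section IX.a (Subject recruitment & screening) describes the clinic's patients and derives a pool. It reports over 600 new patients with long-standing injury in the three years to 2008, and adds: "Currently we evaluate and treat over 250 new patients annually". Of the new patients with long-standing injury, "50% are ASIA A and B and of this subgroup, over 10% have a neurological level between C1 and C6". The pool is introduced by "Using projections through 08' and bases of 850 system clients", and the result is that "approximately 85 patients will meet the entry criteria of ASIA A-B, neurological level C1-6 proposed in our study".

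The paragraph then notes that "study entry does not have to be limited to clients already within our ICSCI system" and concludes: "based on this availability, we do not anticipate the recruitment of patients to be a substantive barrier to recruitment for this study". The target is in section IX.b (Target Population): "We plan to enroll up to 30 subjects with an expected accrued number of subjects of 24", the difference being six expected screening failures.

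**The concern.** The phrase introducing the second percentage makes it a share of the ASIA A-B subgroup, so the two percentages should be multiplied. Doing so halves the stated pool. The match between 85 and a plain 10% of 850 suggests that the 50% step was left out.

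If so, an ethics or funding reader sees twice the margin that the inputs guarantee. Filling 30 places from 85 clients means enrolling about a third of them; from 43 it means about seven in ten. The count also covers only injury class and level. The other criteria in section VIII.a, such as "Male, Female, age 18-55, all ethnic groups", still have to be met, and patients must then agree to 96 intervention visits. What is at stake is the credibility of the feasibility statement.

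**Working it through.** **Inputs**, from section IX.a unless noted:
- Base: 850 clients. This matches 600 + 250 = 850 from the same paragraph, although the protocol does not say the base was built that way.
- Share ASIA A or B: 50%.
- Share at C1-C6 within that subgroup: more than 10%, with no upper value.
- Stated pool: about 85.
- Planned enrolment: up to 30, of whom 24 accrued (section IX.b).

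**Trying to reproduce the stated pool.** The formula is base × P(A-B) × P(C1-C6 given A-B).

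| C1-C6 share of the A-B subgroup | Calculation | Pool |
|---|---|---|
| 10% | 850 × 0.50 × 0.10 | 42.5 |
| 12% | 850 × 0.50 × 0.12 | 51.0 |
| 15% | 850 × 0.50 × 0.15 | 63.8 |
| 19% | 850 × 0.50 × 0.19 | 80.8 |
| 20% | 850 × 0.50 × 0.20 | 85.0 |

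At the quoted 10% the figure is not reproduced: 85 / 42.5 = 2.0.

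**Routes that do give 85:**
- 10% of all clients: 850 × 0.10 = 85.
- A larger subgroup share: 85 / (850 × 0.50) = 0.20.
- A larger base at a 10% share: 85 / (0.50 × 0.10) = 1,700, a figure the protocol does not give.

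The first two describe the same patients, because 20% of half the clients is 10% of all of them. The possible slips are therefore these. Either the 50% step was omitted and the pool is at least about 43, or the 10% was an overall share (or 85 was a count) and the description of the denominator is loose. Nothing in the documents decides between them.

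**Effect on feasibility.** Share of the pool needed from the clinic alone:
- Pool of 42.5: 30 / 42.5 = 71% to enrol; 24 / 42.5 = 56% to accrue.
- Pool of 85: 30 / 85 = 35%; 24 / 85 = 28%.

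**Effect on the statistics.** The power paragraph in section XI.c.3 bases its choice of 24 on earlier FES studies of muscle mass and cardiovascular conditioning. The pool appears neither there nor in the data analysis paragraph.

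**The case for a change.** The strongest case for acting is that two statements in one paragraph do not fit together, the gap is twofold, and one check of the source followed by a wording change would settle it. Describing a 20% share as more than 10% would be odd, so the open-ended wording is a weak defence of 85. The change in the fraction needed, from 35% to 71%, is not trivial for a demanding schedule. The further criteria and consent could bring the clinic's own supply below 30.

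The inconsistency stands: 85 cannot be derived from the inputs given. The rest carries less weight. The floor of 43 does not contradict 85; it shows only that 85 is unexplained. The percentages describe new patients while the base is system clients, which adds doubt about what should be multiplied. Writing 43 into the text by default could replace a correct number with a wrong one. The sentence claims only class and level, so leaving the other criteria out is not an error in it. How far those criteria shrink the pool cannot be computed from the documents, and the plan does not depend on the clinic alone: section IX.a provides for flyers at outside facilities, websites and physician referral.

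**Conclusion.** The concern is right that about 85 does not follow from the stated percentages. They give a floor of 42.5, and 85 needs either 10% of all clients or 20% of the ASIA A-B subgroup. It is not right to conclude that 85 is the wrong number, because the documents leave open which statement is misworded.

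No change to the plan follows. This is a clerical slip in a background estimate, and resolving it either way leaves the sample size, randomisation, visits, outcomes and analysis as they are. The feasibility conclusion also holds on the lower figure, since about 43 exceeds 30 and recruitment extends beyond the clinic. That rests on two assumptions: that the percentages for new patients apply to the 850 clients, and that outside recruitment supplies any shortfall left by the remaining criteria and consent. The second is not quantified in the protocol, but correcting the 85 would not quantify it either.

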Most research groups study the acute phase of injury [29]. But Kennedy Krieger's International Center for Spinal Cord Injury (ICSCI) is developing and applying treatments for long-standing SCI. Its central focus is **Activity-Based Restoration Therapies (RT)**, [30], which have been shown to reduce the risk of cardiovascular disease and diabetes and to lower the incidence of the medical complications of SCI [4, 30]. However, recent research from our group and others has raised the captivating idea that enhancing activity in regions of the nervous system that become dormant after SCI might be critical for spinal cord regeneration [30, 31]. How does functional electrical stimulation enhance neuro-recovery is not entirely clear, but there is evidence that the sensory afferent input provided by peripheral electrical stimulation provides drive to the spared CNS, altering electrophysiological parameters of spinal motor pattern-generating circuitry [32-34], altering amino acid neurotransmitter levels in the spinal cord (glycine and taurine) [35], and altering blood flow, both peripherally and centrally [36, 37]. Direct electrical stimulation of peripheral neuron cell bodies increases BDNF and TrkB expression and leads to axonal regeneration [38-41].

To build on our success with clinical trials that combined leg cycle ergometry with FES of paralyzed muscles [4, 31, 42], we propose ***to determine whether FES, a major component of RT, can promote regeneration and functional recovery by enhancing neural activity through external electrical stimulation***. The studies will be performed by field leaders, scientists, clinicians, and therapists in ICSCI's three major divisions, which are housed at the same location. With their collective expertise in clinical care, regeneration research, magnetic resonance imaging, and clinical trials, these experts are superbly equipped to perform all of the *in vitro*, *in vivo*, and imaging studies proposed here and to disseminate RT methodology to military and civilian rehabilitation specialists across the United States.

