The study subjects will engage in an A (upper extremities FES assisted ergometry)-B (upper extremities non-FES assisted exercises) type protocol intervention in which they undergo either 4 months of FES assisted upper extremity ergometry followed by 1 month wash out period, then by 4 months of a specific, individualized, non-FES assisted exercise regimen (strengthening, stretching, splinting) or 4 months of an upper extremities non-FES assisted exercise protocol followed by 1 month wash out period, then by 4 months of FES assisted upper extremity ergometry. 12 subjects randomly selected will start with the FES assisted intervention and the other 12 subjects will start with the non FES assisted regimen. FES will be delivered using the RT300-SLSA Cycle Ergometer, Restorative Therapies, Inc. The subjects will be assessed using a battery of physical and neurological indicators before starting the intervention (time 0), after completing first 4 months of intervention (4 months), after the 1 month wash out (5 months), after completing the second 4 month of intervention (9 months) and 3 months after completing the last intervention (12 months). The evaluator will be blinded to group assignment, but we cannot use true blinding due to the intervention's sensory component. The Study Time Line is found in Figure 1.

[figure not shown]

Figure 1: Study Time Line

(1) Assessment:

The tests listed below will be performed for all subjects. The data collection schedule in Table 1.

a) Neurological Exam: This is a routine exam performed to rule out any associated lower motor neuron/peripheral nerve injury in the C1-C6 levels. Subjects will undergo testing of the deep tendon reflexes at the biceps, brachio-radialis and triceps level. This involves tapping of each specified muscle tendon with a neurologic reflex hammer.

b) Fast Urine Pregnancy Test: This is a routine exam performed for women of child bearing age who do not take any birth control prophylaxis.

c) Severity of gleno-humeral subluxation: This is a routine exam performed to assess shoulder subluxation. The space between the glenoid and head of the humerus can be visualized on plain X-rays and measured, in centimeters, to grade severity. This test is done bilaterally.

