- 1] allows the stimulation of our proposed list of upper extremity muscles (supraspinatus; infraspinatus; teres major and minor; anterior, middle, or posterior deltoid; biceps; and triceps), which is more than the standard set of muscles (bilateral biceps, triceps and supraspinatus).
- 2] allows to change the timing of the stimulation (On/Off) to produce a smooth cycling motion.

4. FDA approved use description:

The device FDA indication for use are:

1. Relaxation of muscle spasms
2. Prevention or retardation of disuse atrophy
3. Increasing local blood circulation
4. Maintaining or increasing range of motion

5. IDE Info:

Not applicable

c. Study Statistics

1. Primary outcome variable.

Independent Variables

FES or no FES

Dependent Variables: to be measured at 0, 4, 5, 9 and 12months

Severity of gleno-humeral subluxation, measured by X-ray (not measured at 5 months).

Spasticity of the pectoralis, biceps, triceps, and long finger flexor muscles, measured with the Modified Ashworth.

Functional movement of the shoulder, measured with the Capabilities of the Upper Extremity (CUE) test.

Hand function, measured with the Jebsen-Taylor Hand Function (JTHF) and Box and Blocks (BB) tests.

Upper limb function measured with the Action Research Arm test (ARA) test.

Range Of Motion of the upper extremity joints (of the shoulder, elbow, wrist, and fingers/thumbs), measured with goniometry.

Pain, measured with the Numerical Rating Scale (NRS).

Neurological function, measured with the American Spinal Injury Association (ASIA) exam.

2. Secondary outcome variables.

Not applicable

3. Statistical plan including sample size justification and interim data analysis.

Data Analysis: Data will be collected in accordance with each instrument's standardized instructions, with the evaluator being blinded to group assignment. To obtain consistency and facilitate interpretation of the data, we will use means and standard deviations (SDs) to describe normally as well as non-normally distributed variables. Appropriate post-hoc statistical analysis will be used to compare between group means and repeated measures. Baseline tests of homogeneity will be used *a priori*. If statistically significant differences are found after the subjects are randomized to the two groups, they will be corrected in the post-hoc analysis. Results will be considered significant at $P<0.05$.

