Power analysis: Because upper extremity, FES-assisted ergometry training is a new intervention, we based our power analysis on previously completed studies that looked at the effect of FES on muscle mass (50, 51) and cardio-vascular conditioning (52-56). A sample size of 24 will allow us to detect a mean difference between the pre- and post-measures. Some of our outcome measures (CUE, JTHF, BB tests) have been shown to respond to many types of rehabilitative interventions, and we believe they will be particularly responsive to the type of training used here. One of our goals is to use the data obtained in this study to determine the magnitude of the effect so we can design future trials. If the magnitude is very small, however, it is unlikely to be clinically relevant. We would then be more likely to propose intensifying the intervention (e.g., by lengthening the periods of cycling) than to suggest increasing sample size.

4. Early stopping rules.

* Subject medical status:

- Requires significant hospitalization (that would interfere with physiologic processes proposed to be studied through the protocol, i.e. e-stim) – at the discretion of PI.
- Increased pain (more than 3 points increase on the NRS).
- Increased shoulder subluxation (more than 1 cm).
- Decreased range of motion (more than 15 deg).

* Subject not compliant:

- Fails to follow directions.
- Become pregnant.

XII. LABELING & STORAGE OF DATA & SPECIMENS

All paper study documents are stored in locked cabinets at the Broadwaycampus of the KKI-ICSCI. Access to the locked cabinets is strictly limited to the study team members listed on this protocol. The documents with identifiers (such as the consent forms, phone screening forms, and the document that links the subject study # to the identity of the subject) are stored in a study binder in a separate locked cabinet from hard copy data collection forms.

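### With a one-month washout after a treatment expected to have lasting effects, the plan names no governing contrast, and some contrasts it permits are biased if FES benefit outlasts exercise benefit

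*Combined protocol and SAP*

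**What the plan says.** **Design.** Section XI.a.1 has two sequences. One group receives "either 4 months of FES assisted upper extremity ergometry followed by 1 month wash out period" and then four months of exercise without stimulation; the other takes the same blocks in reverse order. Section IX.b adds: "The 24 accrued subjects will be randomized in 2 groups of 12" and "We are anticipating an attrition rate of 4 subjects maximum". Assessments fall at months 0, 4, 5, 9 and 12. Section VII.b calls the trial within-subject controlled and says the measures at all five times serve to test each intervention's efficacy. Section XI.c.1 makes one exception: "Severity of gleno-humeral subluxation, measured by X-ray (not measured at 5 months").

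**Rationale.** Section VII.a asks whether FES "can promote regeneration and functional recovery by enhancing neural activity through external electrical stimulation". It points to synapse formation, repair of myelin and birth of new cells. It also reports earlier leg-cycling data in which 40% of FES subjects moved up from ASIA A, against 4% of controls. No section justifies a washout of one month.

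**Analysis.** Section XI.c.3 says: "Appropriate post-hoc statistical analysis will be used to compare between group means and repeated measures". Baseline differences are corrected only if statistically significant. "Results will be considered significant at" P<0.05, with no sidedness given. On size: "A sample size of 24 will allow us to detect a mean difference between the pre- and post-measures". The same section wants the effect magnitude in order to design later trials. It says that a very small one would probably lack clinical relevance and would point towards a more intensive intervention.

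**The concern.** A within-subject comparison of two treatments given in turn is unbiased only if whatever the first treatment leaves behind is gone, or is equal in both sequences, when the second is measured. Here the trial's own hypothesis suggests that the FES residue may be the larger. In the FES-first group, retained benefit would then be counted as part of the exercise result.

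The statistical section does not say whether the FES effect will be estimated from month 4 alone, from end-of-period values, from changes within each period, or from group means at month 9 or 12. These contrasts respond differently to carryover, and the choice is left until after the data are seen. The estimate is meant to guide later trials. An effect that looks small because it lasted could therefore be misread as a weak intervention.

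**Working it through.** **The plan's own figure.** The sample size of 24 cannot be reproduced: no effect size, SD, within-subject correlation, power or sidedness is given. Assuming two-sided 0.05 and 80% power, a paired pre-post test detects 0.60 SD of the change with 24 subjects and 0.66 SD with 20. A pre-post change does not identify an FES-versus-exercise contrast.

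**Model (assumed).** Let T be the true FES-minus-exercise effect at the end of a four-month block. Effects are additive, only FES carries over, and the FES-first group retains fractions c5 and c9 of T at months 5 and 9. Period effects are common to both groups and cancel when the two sequences are averaged.

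| Contrast | FES-first contributes | Exercise-first contributes | Estimate / T |
|---|---|---|---|
| End-of-period crossover (months 4 and 9) | 1 - c9 | 1 | 1 - c9/2 |
| Change within period (0 to 4, 5 to 9) | 1 - (c9 - c5) | 1 | 1 + (c5 - c9)/2 |
| First period only (month 4, given month 0) | randomised comparison | randomised comparison | 1 |

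**Numbers.**
- End-of-period: c9 = 0 gives 100%; 0.25 gives 87.5%; 0.5 gives 75%; 0.75 gives 62.5%; 1 gives 50%.
- Change within period: (c5, c9) = (0, 0), (0.5, 0.5) or (1, 1) gives 100%; (1, 0.5) or (0.5, 0) gives 125%; (1, 0) gives 150%.
- Parallel comparison at month 9: both groups have had FES. Current FES minus current exercise is 1 - c9 of T, which is zero if the effect lasts fully. At month 12 both groups have likewise had both treatments.
- First period: 100% whatever the retention. Simulation (20,000 trials, 12 per sequence) gave 0.996 to 1.002 of the truth across five retention patterns.

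**If exercise also carries over.** Let LF and LE be the amounts of FES and exercise benefit still present at month 9 in the groups that had them first. The end-of-period estimate becomes T - (LF - LE)/2, so only the difference in carryover matters.

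**Subluxation.** There is no month-5 film. If the month-4 film served as the second-period baseline, the estimate would be the average of 2 - c9 and 1, that is (3 - c9)/2: 100% at c9 = 1 and 150% at c9 = 0. End-of-period values go from 100% at c9 = 0 to 50% at c9 = 1. Neither is safe without knowing c9, and adjusting for month 0 does not remove carryover that arises later.

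**Precision (two-sided 0.05, 80% power, no baseline adjustment).**
- First period, 12 per arm: (1.960 + 0.842) x sqrt(2/12) = 1.14 SD by normal approximation, 1.20 SD by the t distribution.
- First period, 10 per arm (24 - 4 = 20, split evenly): 1.25 and 1.32 SD.
- Power against 0.8 SD: 47% with 12 per arm, 40% with 10.
- Crossover, end-of-period values, N = 24, assumed within-subject correlation 0.5: the standard error is sqrt(2 x 0.5/24) = 0.204 SD. Power at 0.8 SD is 96% without carryover and 47% at c9 = 1. At correlations 0.7 and 0.9 the halved effect still has 68% and 99% power, but the estimate remains halved.
- A between-sequence test for carryover of 0.8 SD has about 16% to 19% power.

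**The case against.** The strongest reply is that the bias is conditional. The documents give no retention fraction. If the FES effect is wholly permanent and additive, change from month 5 is unbiased. The comparator is four months of supervised exercise at the same weekly frequency, and its own lasting benefit would offset part of any bias. The regeneration language is background rationale, whereas the outcomes include pain, spasticity, range of motion and subluxation, and section XIV lists muscle and conditioning effects as the possible benefits. For those, persistence beyond a month is not documented. All of this stands. It limits the claim to differential carryover, and it means the documents do not show one month to be too short. They simply do not justify it.

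A second reply is that comparing group means at the scheduled times already includes month 4, which is free of carryover. That is true of the data. The plan does not, however, single out that contrast, and picking it afterwards loses the protection of pre-specification.

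A third is that the first-period comparison is imprecise. It is, and that is a real cost. A preliminary carryover test is no way round it, given its low power.

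**Conclusion.** The point holds as a gap in pre-specification with a quantifiable consequence. Under the stated model, crossover contrasts that the plan permits range from about 50% to 150% of the true FES effect, and a month-9 parallel comparison can fall to zero. The first-period comparison is unaffected. The size rests on assumed retention, additivity and carryover from FES only.

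A reader might infer more than the documents support:
- **That the trial cannot tell no effect from a lasting one.** Month 4 is a randomised, carryover-free comparison and is measured for every listed outcome.
- **That the trial's estimate is biased.** No estimate is named, and some permitted ones are unbiased under some retention patterns.
- **That the month-5 data have no role.** Section VII.b gives them a general one; XI.c.3 does not say how they enter the analysis.
- **That the month-4 film must never serve as the second-period baseline for subluxation.** The plan does not propose doing so, and under full retention that choice is unbiased while end-of-period values are halved.

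**What to change.** Amend section XI.c.3 as follows.

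1. For every outcome, including subluxation, name the randomised first-period comparison (month 4 adjusted for month 0, FES-first against exercise-first) as the governing estimate of the FES effect. Do not make this conditional on a carryover test. Adjust for month 0 whether or not the groups differ significantly at baseline, in place of the present conditional rule.
2. Report the crossover estimate, with period and sequence terms, as supportive only.
3. Where month 5 is measured, report month 5 minus month 0 by sequence descriptively. Practice and period effects can also move this difference, so it is not a pass-or-fail test.
4. State that a null crossover estimate alone is not read as absence of effect.
5. For subluxation, treat any crossover estimate as supportive and state how it depends on carryover.

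No treatment, washout, visit or film changes, and all the data are already scheduled. The cost is lower precision: about 1.2 SD detectable with 12 per arm, or 1.3 SD with 10, before any gain from baseline adjustment. The second figure is pessimistic if some dropouts leave after month 4. This settles which contrast governs; it does not address multiplicity across the listed outcomes, which needs its own rule.
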